sensitive to clinical change, and unlike most other measures of suicidal ideation, higher scores on the BSS are associated with death by suicide. While there is no established BSS cutoff score to classify suicide risk as high, low, or none, there is evidence that higher scores on the BSS correspond to more severe suicidal ideation.^{2,39} There is evidence that an improvement of five points or more on the total BSS scores may be clinically relevant.²

Secondary Outcome (Patient Engagement): We will measure patient engagement in treatment at baseline and at follow-up assessments. Patient engagement is a complex phenomenon to measure.⁴⁰ The term 'patient engagement' encompasses various aspects of care related to a patient's motivation and intent to be an active participant in addressing their healthcare needs.⁴⁰ To date, there is no agreed-upon measure in the literature that incorporates all aspects of the experience of 'patient engagement.⁴⁰ In the field of mental health, there is some notion that 'patient engagement' should mean that a patient experiences collaborative care, feels supported during their treatment, and adopts 'good practices' or behaviors that support their overall well-being.⁴⁰⁻⁴¹ Therefore, only assessing whether a patient attended a mental health appointment may not adequately reflect treatment engagement. There is also evidence that symptom severity can preclude patients from engaging in care.⁴² Pfeiffer *et al.* found that, despite improvements in timely outpatient follow-up after VA psychiatric hospitalization, there were no significant changes in readmission or antidepressant treatment.⁴³ In fact, Bernet *et al.* found that appointment intensity was higher in Veterans who reattempted suicide after discharge versus those who did not reattempt.⁴⁴ Thus, we conceptualize that engagement includes continuity of care and activation.

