Statistical Analyses: To maintain blinding, the statistician who is otherwise not directly involved in the study will conduct the analysis based on the intention-to-treat principle. Below, we have outlined the specific analysis plan for assessing each of the primary and secondary aims of interest of this study. We will assess for statistically significant differences in baseline study characteristics such as age, sex, race, and mental health diagnosis, between study arms using *t*-tests for continuous measures and chi-squared tests for dichotomous variables. We will report these results using 95% confidence intervals (CI) and *P*-values. We will define statistical significance as a *P*-value < 0.05. If we identify any variables for which there are significant differences across study arms, we will control for these confounders in the analysis of the aims.

Specific Aim 1: We will generate descriptive summary statistics (e.g., means and standard errors, medians) and graphical displays for the BSS total scores at baseline and at each of the follow-up assessments. For each of the four acute care settings included in our study, we will perform simple statistical tests. First, we will use a repeated measures analysis of variance (ANOVA) test to assess for changes in continuous variables in the first three months after discharge. Second, if the repeated measures ANOVA suggested a significant difference in means across time, we will perform a post-hoc, pair-wise comparison of means at baseline and one- and three-month follow-up using a two-sample t-test.

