We will perform a more complex analysis for the entire study sample at the end of the four years because we will have adequate power to do so. The following outlines are specific approach: Based on available evidence, we hypothesize that the VA BIC program plus standard hospital discharge care will lead to a significant reduction in suicidal ideation after discharge from an acute care setting. We believe that the effect of VA BIC on suicidal ideation will be the greatest at the three-month follow-up because the greatest intensity of follow-up care provided through VA BIC occurs within the first three months after discharge. We will generate descriptive summary statistics (e.g., means and standard errors, medians) and graphical displays for the BSS total scores at baseline and at each of the follow-up assessments. Because BSS scores are typically over dispersed, it is not appropriate to use standard parametric statistics. Therefore, we will treat the BSS scores as count data and use negative binomial regression. Specifically, we will use a generalized linear mixed model. We will consider allocation of study arm (categorical measure) and time (continuous measure) as fixed effects. Random effect will be used to account for correlation that arises from repeated measures of the same individual. We will assume a linear effect and model changes in suicidal ideation over time. We will calculate 95% CI and P-values and will define a *P*-value of < 0.05 to be statistically significant. We will use the maximum likelihood ratio to account for any missing data.

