Specific Aim 2: First, we will perform an analysis to demonstrate whether there are greater improvements in patient engagement, hopelessness, and perceived connectedness over time in patients assigned to the VA BIC intervention versus control condition at one, three months after discharge. For continuous variables measuring patient engagement (PIH, Hopelessness, Regularity of Care, Continuity of Care across Organizational Boundaries, and Intensity of Care) and perceived connectedness (INQ-15), we will generate descriptive summary statistics (e.g., means and standard errors, medians) and graphical displays for each measure at baseline and at each of the follow-up assessments. Second, using analysis of covariance (ANCOVA), we will calculate mean differences in scores for each of our continuous measures at the one-and three-month follow-up, as well as the associated 95% confidence intervals and *P*-values. For the categorical measure of disruptions in care, we will use chi-squared tests to compare the proportion of patients experiencing disruptions in care between the two study arms at one- month and three-months after discharge.

Specific Aim 3: While suicide deaths and suicide attempts are important clinical endpoints, this single-site trial will not be powered to detect a statistically significant effect between study arms. Furthermore, because we assume that few events will be observed in either arm, we plan to summarize our findings by providing basic descriptive statistics regarding the number of events in each arm at one-and three-month follow-ups.

Randomization: Prior to the start of study enrollment, the statistician will independently prepare allocation cards using a permutated block schedule. The advantage of this approach is that it ensures that an equal number of participants are assigned to each arm.⁵⁶ The statistician will the put these cards into sealed, opaque, numbered envelopes. The box of envelopes will be stored in a locked cabinet in the study coordinator's locked office.

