Sample Size: Because of our promising pilot work,¹ we believe it is appropriate to choose suicidal ideation as our primary outcome. In our pilot study, which included nine Veterans undergoing the VA BIC intervention, we found a greater than five-point improvement in the Beck Scale for Suicidal Ideation (BSS) over the three months following inpatient mental health discharge. Five points is a clinically meaningful improvement on the BSS as it represents the mean difference in suicidal ideation between ambulatory and hospitalized psychiatric patients.² Furthermore, with this sample size and level of improvement, we were able to demonstrate a significant difference in improvement in suicidal ideation compared to a matched group of historical controls participating in a post-mental health discharge qualitative study.^{1,3} Therefore, we will have sufficient power to show a clinically meaningful improvement in suicidal ideation overall and for each of the four high-risk care transition scenarios at one and three months after discharge if we enroll a total of 100 veterans (25 per transition scenario) over 3 years.

Study Population and Recruitment

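### Within each setting, the primary BSS outcome is tested by ANOVA and t-tests, which the plan itself calls unsuitable for BSS, and neither test is written as a comparison of the arms

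*Combined protocol and SAP*

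**What the plan says.** All of this stands in Statistical Considerations of the combined protocol and SAP.

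- **Per setting (Specific Aim 1, opening paragraph).** "For each of the four acute care settings included in our study, we will perform simple statistical tests". The first is stated as: "we will use a repeated measures analysis of variance (ANOVA) test to assess for changes in continuous variables", over the three months after discharge. If it shows a difference across time, pairwise comparisons of the baseline, one-month and three-month means follow, by two-sample t-test. Arm is not mentioned in either step.
- **Whole sample (Specific Aim 1, next paragraph).** "Because BSS scores are typically over dispersed, it is not appropriate to use standard parametric statistics". BSS is therefore treated as a count in a negative binomial mixed model with arm and time as fixed effects. This more complex analysis is kept for the full sample on grounds of power.
- **Size (Sample Size).** The plan makes this claim: "we will have sufficient power to show a clinically meaningful improvement in suicidal ideation overall and for each of the four high-risk care transition scenarios". The claim is conditional on enrolment: "if we enroll a total of 100 veterans (25 per transition scenario) over 3 years".
- **Allocation (Randomization).** Permuted blocks are used because "it ensures that an equal number of participants are assigned to each arm".
- **Threshold (opening paragraph).** "We will define statistical significance as a *P*-value < 0.05".

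No confidence interval is specified for the per-setting BSS tests. The interval sentence in the opening paragraph follows the baseline-characteristics comparisons. Those further on belong to the mixed model and to the Aim 2 ANCOVA.

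**The concern.** Over-dispersion is a property of the score. It is present among 25 patients as much as among 100, and the smaller sample gives normal-theory methods less protection. The plan thus uses the class of method it rejects where that method has the least support.

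Setting-level results carry weight. Specific Aims/Purpose makes later dissemination depend on effectiveness in at least one scenario and wants to steer facilities to the populations most likely to benefit. The deliverables list has each setting analysed, and the first two manuals finalised from their results, before the data are combined in Year 4. The pooled model has no setting term, so it gives no setting-specific estimate. A setting's own answer therefore comes from the ANOVA and t-test step. If that step tests time rather than arm, improvement that would have happened under either assignment can be read as an effect of VA BIC.

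**Working it through.** **1. Patients per arm.** 25 / 2 = 12.5, so 12 and 13 at best. The block size is not stated, and an incomplete last block could widen the gap slightly.

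**2. The plan's own figure.** The claim of sufficient power at 25 per setting cannot be reproduced: there is no SD, no numeric power and no between-arm difference. The 5 points are a pilot improvement, also described thus: "There is evidence that an improvement of five points or more on the total BSS scores may be clinically relevant". With power = Φ(5 / (SD·√(2/12.5)) − 1.96), an assumed SD of 4 gives 88%, SD 6 gives Φ(5/2.4 − 1.96) = Φ(0.12) = 55%, and SD 10 gives 24%. Any numerical check below therefore rests on assumed spread.

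**3. What the gate tests.** Simulated: 25 patients, both arms improving equally, so no arm effect. Scores are gamma-mixed Poisson, capped at the BSS maximum of 38.

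| Assumed k | Correlation, baseline with 3 months | ANOVA on time, P < 0.05 | Two-sample t, baseline vs 3 months | Paired t |
|---|---|---|---|---|
| 0.5 | 0.72 | 42% | 6% | 47% |
| 1 | 0.60 | 54% | 20% | 59% |
| 2 | 0.46 | 62% | 41% | 67% |

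The visit means here are 12, 8 and 7. Over other assumed visit means, the ANOVA rejected in 36% to 100% of trials. These are correct rejections of no change over time; they say nothing about VA BIC.

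The two-sample test also ignores pairing. With equal variances, the true variance of a within-patient mean change is 2σ²(1 − ρ)/n, while the test uses 2σ²/n. The standard error is too large by 1/√(1 − ρ): at ρ = 0.60, 1/√0.40 = 1.58.

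**4. If the t-test is taken to compare arms.** Simulated: negative binomial scores, k = 0.3 to 2, capped at 38, 12 vs 13 patients, 50,000 trials per case.

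| Arm means before the cap | Coverage of nominal 95% t-interval | Rejection rate under no difference |
|---|---|---|
| Equal (3, 5 or 10) | 95.2%–96.6% | 3.4%–4.8% |
| 8 vs 3, 10 vs 5, 12 vs 7 | 90.9%–94.3% | – |
| 5 vs 1 | 84.8%–91.5% | – |

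The cap shrinks the 5-point differences to between 2.9 and 5.0 points. A second run of the 5-point cases gave 92% to 95%.

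**5. Candidate replacements at this size.**

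- Negative binomial regression with Wald intervals (k = 0.5 or 1): coverage 92.2% to 94.7%, false positive rate 5.3% to 7.8%. At 10 vs 5 it covers 93.6% and 92.8%, against 93.5% and 93.6% for the t-interval.
- Percentile bootstrap: 89% to 91% for 5-point differences. At 5 vs 1 it gives 85% to 88%, against 87% to 91% for the t-interval in the same run.
- Re-randomisation test of the between-arm BSS difference: false positive rate 4.5% to 5.3%.

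**6. The pooled model's arm term.** With arm and time but no interaction, and log-scale effects of 0, d and d at the three visits, equal weighting gives (0 + d + d)/3 = 2d/3. The baseline visit dilutes the effect by about a third, so this contrast should not be carried into the settings unchanged.

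**The case against.** Simple tests at n = 25 are a stated choice: the plan keeps the complex model for the sample it believes can support it. The t-test is robust here, holding its level under every equal-mean case tried, and the count model with Wald inference does no better at this size. Ground East patients also receive medians and graphical displays, and they enter the Year 4 analysis. A two-sample t-test may well have been meant as arm against arm.

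Much of this stands. A reader might infer that the per-setting confidence intervals are wrong. The documents do not support that: no such interval is specified, and a t-interval would usually fall short by a few points, by an amount that depends on a dispersion they do not give. A reader might also infer that the t-test is invalid, or that Ground East gets nothing but the rejected method; neither is so.

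Two things remain. Power is no reply to over-dispersion, and the plan also claims sufficient power within each setting. And if the t-test was meant between arms, the text does not say so and still makes it conditional on a test of time.

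**Conclusion.** The point holds as an internal contradiction about the primary outcome, joined to a per-setting test that does not address the treatment question. Both can be read directly from the text and need no assumption. The second is the more serious: a setting could pass the gate in 36% to 100% of simulated trials with no arm effect.

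The distributional damage is smaller. Under assumed over-dispersion, a t-interval between arms would cover about 91% to 95% for 5-point differences before the cap, and less in extreme cases such as means of 5 vs 1. The level of the t-test is acceptable. These figures assume negative binomial scores, no dropout and two-sided testing at 0.05. Confidence is high on the contradiction and moderate on the size. It should be corrected before Ground East data are analysed.

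**What to change.** Reconcile the two paragraphs of Specific Aim 1, and replace the per-setting text as follows.

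- Drop the ANOVA gate and the pairwise t-tests over time.
- In each setting, compare BSS between arms at one and three months, adjusted for baseline BSS. Take the P-value from re-randomisation, permuting arm labels within the blocks of the allocation schedule.
- Report the mean difference in points, with an interval obtained by inverting that test. Label it approximate when the arms differ in spread, because inversion assumes a constant shift.
- Do not use a percentile bootstrap or a negative binomial Wald interval at this size; neither is more accurate than the t-interval.
- If the count model is added per setting as a supporting analysis, use a post-baseline arm contrast: an arm-by-time term, or baseline BSS as a covariate.

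The cost is one paragraph, a little programming and access to the block schedule at analysis. P-values will be discrete at n = 25. No extra patients or data are needed.

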Overview of the VA BIC Intervention and RCT Design

As shown in **Figure 1 (see previous page)**, to test the aforementioned hypotheses, we propose to conduct a single-site, assessor-blinded RCT at the WRJ VAMC comparing the VA BIC plus standard psychiatric hospital discharge care to standard psychiatric hospital discharge care alone. The trial will enroll patients 18 years and older who are being discharged from the WRJ VAMC inpatient mental health unit. The primary aim is to determine whether the VA BIC reduces suicidal ideation at one and three months after psychiatric hospitalization. The secondary aim is to evaluate the impact of VA BIC on other important measures of suicide risk including hopelessness, connectedness, fatal/non-fatal suicide attempts and treatment engagement.

Baseline Assessment and Randomization: Prior to the start of study enrollment, the statistician will independently prepare allocation cards using a permutated block schedule. The statistician will the put these cards into sealed, opaque, numbered envelopes. The box of envelopes will be stored in a locked cabinet in the study coordinator's locked office.

The study coordinator will meet with each eligible patient in a private room on GE around the time of discharge. The study coordinator will obtain informed consent from the patient and then administer the baseline assessments, which are described under the outcome measures (see below). The baseline visit will take approximately 90 minutes to complete. After obtaining consent and completing the baseline assessment, the study coordinator will take the next numbered envelope from the box (described above) and open the envelope to determine the patient's assignment. In the event that the patient has been assigned to the intervention, the study coordinator will notify the VA BIC intervention staff in order that the intervention staff can initiate the intervention. Otherwise, the patient will be informed that they have been assigned to usual care.

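### As written, the pooled Aim 1 model gives one arm effect for all visits, so no separate 1-month and 3-month effects, and baseline BSS has no fixed role

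*Combined protocol and SAP*

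**What the plan says.** The pooled analysis is described under Statistical Considerations, Specific Aim 1. BSS totals are treated as counts in a negative binomial generalised linear mixed model. On the fixed part: "We will consider allocation of study arm (categorical measure) and time (continuous measure) as fixed effects". A random effect handles repeated measures on the same person. The text adds: "We will assume a linear effect and model changes in suicidal ideation over time". It writes no arm-by-time term, no categorical visit and no contrast by visit, and it names no coefficient as the test of Aim 1. The hypothesis in the same section is: "We believe that the effect of VA BIC on suicidal ideation will be the greatest at the three-month follow-up". The Sample Size section claims sufficient power, overall and per care setting, at one and three months with 100 veterans.

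BSS is collected at 0, 1 and 3 months. The baseline value precedes allocation: "After obtaining consent and completing the baseline assessment, the study coordinator will take the next numbered envelope from the box". In the pooled analysis baseline BSS appears only in descriptive summaries. The one adjustment rule, under Statistical Analyses, covers variables that differ significantly between arms at baseline: "we will control for these confounders in the analysis of the aims".

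Two nearby analyses mention the follow-up visits. Within each care setting, after a significant repeated measures ANOVA across time, "we will perform a post-hoc, pair-wise comparison of means at baseline and one- and three-month follow-up using a two-sample t-test". For Aim 2, "using analysis of covariance (ANCOVA), we will calculate mean differences in scores for each of our continuous measures at the one-and three-month follow-up".

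**The concern.** This is the final analysis of the primary aim, and the text does not fix which quantity answers it. A model with arm and linear time only cannot separate a 1-month from a 3-month effect, nor show that the effect is larger at three months. The other analyses do not fill the gap. The per-setting t-tests are not pooled, are conditional on another test, and do not say whether arms or times are compared. The ANCOVA at one and three months belongs to the secondary outcomes.

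The role of baseline matters as much. As a response row in a model without interaction, it brings a visit with zero expected arm difference into the treatment effect. If it is left out, the precision it could supply is lost. The same data would then give different answers to Aim 1 according to a choice made at analysis.

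**Working it through.** **Plan's own figure.** The plan gives 100 veterans but no numeric power, SD or correlation, so there is no power figure to reproduce.

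**Step 1, the model as written.** With the usual log link (the link is not stated), log(mean) = b0 + b1·arm + b2·time + u. The arm ratio is exp(b1) at 0, 1 and 3 months alike.

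**Step 2, what the arm effect estimates.** Linear scale, complete data, equal variances and a common correlation r. Let d1 and d3 be the true arm differences at 1 and 3 months; the baseline difference is 0 in expectation.
- Reading A (all three visits are responses, no interaction): (0 + d1 + d3)/3. For d1 = d3, d3/2 or 0 this is 67%, 50% or 33% of d3, so a true 5 points appears as 3.3, 2.5 or 1.7.
- Reading B (1M and 3M are responses): (d1 + d3)/2, which is 100%, 75% or 50% of d3.
- Reading C (arm-by-linear-time was meant): a line through t = 0, 1, 3 with its intercept free. Mean t = 4/3 and the sum of squares is 14/3. For true differences 0, D, D the slope is (4/3)D/(14/3) = 0.286D and the intercept is (2/3)D − (4/3)(0.286D) = 0.286D. The fitted differences are 0.29D, 0.57D and 1.14D. Linear growth (0, D/3, D) is fitted exactly.

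**Step 3, ratio scale.** Negative binomial random-intercept fits to 6,000 simulated patients. Assumed: control means 12/9/8, random-intercept SD 0.5, dispersion 4, no cap at 38.

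| True ratios 0/1/3M | A | B | C at 1M, 3M | Arm by categorical visit, 1M, 3M |
|---|---|---|---|---|
| 1.00/0.80/0.60 | 0.820 | 0.714 | 0.851, 0.608 | 0.800, 0.615 |
| 1.00/0.60/0.60 | 0.738 | 0.596 | 0.766, 0.549 | 0.593, 0.595 |

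**Step 4, power.** Normal approximation, two-sided 0.05, 50 per arm. The 5 points are assumed to be the between-arm difference at 3 months. With s = SD·√(2/50), z is:
- A: [(d1 + d3)/3] / [s√((1 + 2r)/3)]
- B: [(d1 + d3)/2] / [s√((1 + r)/2)]
- baseline-adjusted average: [(d1 + d3)/2] / [s√((1 + r)/2 − r²)]
- baseline-adjusted 3-month contrast: d3 / [s√(1 − r²)]

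Example: SD 8, r = 0.5, d1 = d3 = 5, so s = 1.6. A: 3.33/1.306 = 2.55, power 72%. B: 5/1.386 = 3.61, 95%. Adjusted average: 5/1.131 = 4.42, 99%. Adjusted 3-month: 5/1.386 = 3.61, 95%.

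At SD 10 (s = 2.0), r = 0.5, power in %:

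| Analysis | d1 = 5 | d1 = 2.5 | d1 = 0 |
|---|---|---|---|
| A | 53 | 33 | 18 |
| B | 82 | 58 | 30 |
| Adjusted average | 94 | 76 | 42 |
| Adjusted 3-month | 82 | 82 | 82 |

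At SD 10 with equal effects, A against the adjusted 3-month contrast is 68% v 72% at r = 0.2 and 46% v 94% at r = 0.7. Break-even for A is at r of about 0.15.

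**Step 5, the adjustment rule.** Under randomisation, baseline BSS differs significantly at 0.05 in about 5% of trials, so the rule would seldom bring it in.

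**The case against.** The strongest reply is that the sentence about modelling changes over time implies an arm-by-time term. That may be so. A reader might infer that the plan definitely forces one arm ratio; the documents support this only for the literal list of fixed effects. But no interaction is written, and a linear one would still misfit an effect already present at one month (Step 2, reading C).

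A second reply concerns the time points. A reader might rely on the stated primary aim, to "determine whether the VA BIC reduces suicidal ideation at one and three months after psychiatric hospitalization". That sentence describes the Ground East trial, which is analysed by the per-setting tests. The general Aim 1 speaks only of ideation after discharge, which an average effect could answer. The support for separate pooled effects is instead the Sample Size claim, which links the overall result to one and three months, together with the expected 3-month peak. That peak is a belief about timing, not a named primary contrast.

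Third, a shared follow-up effect is not a defect in itself. With equal effects, the baseline-adjusted average beats the 3-month contrast (94% against 82% at SD 10, r = 0.5). This stands: preferring three months is partly a choice.

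Fourth, the sizes rest on assumed inputs, and the 5 points come from a within-group pilot change. This also stands; the power figures are illustrations. A reader might also infer a risk of false benefit. There is none here: with no effect at any visit the arm coefficient is centred on zero.

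**Conclusion.** The point holds as a defect of specification with a better method at hand. Read literally, the pooled model cannot give the 1-month and 3-month effects separately, baseline BSS has no routine role, and the deciding coefficient is not named. If baseline is a response row without interaction, a real effect is underestimated, to 67%, 50% or 33% of the 3-month effect on a linear scale. If only follow-ups are responses there is no dilution, but the estimate is an average and loses baseline precision.

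The effect on power cannot be fixed from the documents. It runs from negligible (low correlation, equal effects) to severe (high correlation, or little effect at one month). When the 1-month effect is at least half the 3-month effect, most of the loss comes from baseline dilution or from omitting baseline adjustment, not from the shared follow-up effect. If there is no effect at one month, averaging itself costs most. These statements assume complete data, equal variances and a common correlation. The conclusion that one coefficient serves all visits needs none of these.

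**What to change.** Keep the negative binomial mixed model and state one of two forms: baseline BSS as a covariate with 1M and 3M as responses, or all three visits as responses with a common baseline mean in both arms. In either, enter visit as categorical with arm-by-visit terms and report the arm contrast at 1 month and at 3 months. State in advance whether the 3-month contrast or the average of the two decides Aim 1. Three months fits the stated hypothesis but is not always the more powerful choice.

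The cost is SAP wording. No new data are needed. Fixed parameters rise from 3 (intercept, arm, time) to 5, or to 6 if a baseline arm term is kept. The pooled analysis is a Year 4 deliverable and the protocol already foresees amendments, so the change can be made before that analysis.
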